7.6.1 Adverse Events

Summary information (the number and percent of subjects by treatment) will be tabulated for:

- TEAEs, including clinical and laboratory AEs

- Treatment-related AEs
- TEAEs by severity
- Treatment-related AEs by severity
- SAEs
- AEs leading to discontinuation

Summaries will be presented by treatment groups and categorized by System Organ Class and Preferred Term. The frequencies of AEs displayed will be the crude rates that represent the number of subjects experiencing AEs divided by the total number of subjects.

It should be noted that all laboratory data sent to and analyzed by the NYU laboratory will be reported to the investigator. However, only those laboratory abnormalities meeting the protocol-defined criteria of an AE (ie, those that require clinical intervention or further investigation beyond ordering a repeat [confirmatory] test) should be reported as AEs in the appropriate CRF, whether they were analyzed by the NYU laboratory or another laboratory.

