Study Product, Dose, Route, Regimen:	
Ataluren (powder for oral suspension)
 
Dose: 3 times per day (TID; 10 mg/kg, 10 mg/kg, and 20 mg/kg morning, midday, and evening, respectively)
 
Titration: None
 
Maximum dose: TID (10 mg/kg, 10 mg/kg, 20 mg/kg morning, midday, and evening respectively)

Duration of Administration:	
Each subject will receive a total of 12 weeks of active drug (ataluren) and 12 weeks of placebo, in a masked fashion

Reference Therapy:	
None

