1.5 Study Design

[figure not shown]
Crossover designs are usually statistically efficient and thus require fewer subjects. Additionally, the influence of confounding covariates is reduced because each crossover subject serves as his or her own control. A 12-week treatment period with ataluren provides sufficient time to assess changes in the subject's seizure activity and QOL while still allowing appropriate monitoring of the subject. Due to the lack of effective alternative treatment, subjects and their parents/legal guardians will be motivated to participate in this study. Therefore, we expect a low dropout rate.

The study to be conducted is a Phase 2 interventional study which includes the following: Screening (Week -4 to Week 0/Day 1), Treatment Period 1 (Week 0/Day 1 to Week 12), Washout Period (Week 12 to Week 16), crossover to Treatment Period 2 (Week 16 to Week 28), and a Follow-up visit after 4 weeks. Subjects who complete this study may be eligible to enroll in a 96-week open-label extension study (Week 28 to Week 124). A Follow-up visit is to occur 4 weeks after the last dose of study drug for all subjects, regardless of whether a subject discontinues prematurely or completes the End-of-Study (EOS) visit and/or the open-label extension. For subjects who enroll in the extension study, Follow-up is scheduled to occur at Week 128. The opportunity to enroll in the extension study will be explained to subjects during the initial study informed consent by the site investigator; subjects enrolling in the extension study do not need to re-consent.

The treatment period in this study ends at Week 124 (Visit 11). However, for subjects that want to continue on study medication beyond Week 124, PTC Therapeutics will continue to supply drug. All subsequent visits will be standard of care and any blood work will be at the discretion of the investigator. A follow up visit for subjects who do not want to continue will be scheduled 4 weeks following the last dose. Access to study drug will continue until commercial availability of ataluren for this indication or until a positive risk-benefit assessment in this indication is not demonstrated whichever is first.

The study design is shown in Figure 2. The Schedule of Events is provided in Table 1.

Figure 2: Study Design

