b. During Treatment Period 2, subjects will crossover and begin receiving masked study drug opposite of what they received during Treatment Period 1 (ie, subjects previously receiving masked ataluren will now receive placebo and subjects previously receiving placebo will now receive ataluren).

01 Aug 2019

- c. The EOS visit (Week 28) will be completed for all subjects who complete or discontinue early from Treatment Period 1 and 2. Subjects who complete the EOS visit may continue in the open-label portion of the study at Week 28, otherwise a follow-up visit should be scheduled after 4 weeks.
- d. All subjects enrolling in the open-label extension study will receive ataluren 10, 10, 20 mg/kg 3 times per day for 96 weeks.
- e. The Follow-up visit is to occur 4 weeks after the last dose of study drug, regardless of whether the subject discontinues prematurely or completes the EOS visit and/or the open-label extension.
- f. Visit 2 is considered the Baseline Visit. Visit 2 must occur no sooner than 28 days and up to 42 days after Visit 1. All study and laboratory assessments must be completed prior to the first dose of study drug administration.
- g. If the subject begins but does not complete the open-label extension, complete EOT (Week 124).
- h. The first dose of study drug should be given in the clinic at Visit 2 (Baseline), Visit 5 (Week 16), and, if applicable, in the open-label extension at Visit 7 (Week 28).
- i. The last dose of study drug prior to Visit 4/Week 12 (Treatment Period 1) and Visit 7/Week 28 (EOS Visit) should be taken the night before, at home. No morning dose should be taken prior to the clinic visit.
- j. Serum HCG samples taken only for female subjects of childbearing potential
- k. Ataluren plasma PK will be assessed at 0 hr (pre-dose) at Visit 5/Week 16 and at 0 hr (pre-dose) and 2 hr post-dose at Visit 3/Week 6 and Visit 6/Week 22.
- l. AED plasma PK will be assessed at 0 hr (pre-dose of AED, including but not limited to valproate, clonazepam, lamotrigine, topiramate, and levetiracetam).

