7.6 Safety Analyses

All safety presentations will be based on the ITT Population and will be based only on data included in the analysis period of interest. Listings of all AEs will also be based on all available data at the scheduled analysis time point. Adverse event and SAE summaries will also be presented for the following periods:

- Up to the end of Visit 4 (Week 12)
- Up to the end of Visit 7 (Week 28, EOS Visit)
- Between the start of Week 17 and the end of Week 28.
- Up to the end of the open-label extension (Week 124, if applicable)
- Between the start of Week 29 and the end of Week 124 (if applicable).

Additional frequency tables summarizing the occurrence of AEs and SAEs after the end of the analysis period of interest will also be provided. All AEs and SAEs will be summarized by treatment group. Marked laboratory abnormalities will also be descriptively summarized. No statistical tests will be performed for AEs or laboratory marked abnormalities.

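### In the cumulative AE summary to Week 124, crude percentages by treatment received would set up to 108 weeks of ataluren against 12 weeks of placebo

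*Combined protocol and SAP*

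**What the plan says.** Section 7.6.1 tabulates "the number and percent of subjects by treatment" and defines the frequencies as "crude rates that represent the number of subjects experiencing AEs divided by the total number of subjects". Section 7.6 adds that "All AEs and SAEs will be summarized by treatment group", bases every safety presentation on the ITT Population (all randomized subjects, Section 7.3), and rules out statistical tests for AEs.

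Section 7.6 lists five windows: to Week 12, to Week 28, Weeks 17–28, Weeks 29–124, and a cumulative one, "Up to the end of the open-label extension (Week 124, if applicable").

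On exposure, the synopsis states: "Each subject will receive a total of 12 weeks of active drug (ataluren) and 12 weeks of placebo, in a masked fashion". Section 1.5 describes a "96-week open-label extension study (Week 28 to Week 124"), and a footnote to Table 1 in Section 6.1 says: "All subjects enrolling in the open-label extension study will receive ataluren 10, 10, 20 mg/kg 3 times per day for 96 weeks".

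No AE rate per unit of time is planned. Duration of ataluren exposure is tabulated separately in Section 7.5.3 and is not linked to AE frequencies.

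**The concern.** The share of subjects with at least one event rises with the time they are watched. Two such shares can be compared only if the observation times are similar. The extension adds time on ataluren and none on placebo, so a cumulative by-treatment table to Week 124 would largely show observation time.

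Characterizing safety is a secondary objective in Section 2.1. Section 7.1 calls it the primary objective, and the title describes a safety and tolerability study. Section 13 plans to publish tolerability findings for the whole series. A side-by-side percentage from this table would probably be read as a drug effect whether or not it is tested.

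**Working it through.** **Exposure.** Extension: 124 − 28 = 96 weeks, matching the stated length. Maximum ataluren: 12 + 96 = 108 weeks. Placebo: 12 weeks. Ratio: 108/12 = 9. Section 4.2 gives 90 days per period instead of 84. That makes the ratio (90 + 672)/90 ≈ 8.5, which changes nothing material.

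**The five windows, if columns mean treatment received:**

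| Window | Planned ataluren v placebo exposure |
|---|---|
| To Week 12 | 12 v 12 weeks, between subjects |
| Weeks 17–28 | 12 v 12 weeks, between subjects |
| To Week 28 | 12 v 12 weeks per completing subject, plus the washout |
| Weeks 29–124 | ataluren only, no placebo |
| To Week 124 | up to 108 v 12 weeks |

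Only the last window carries the imbalance.

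**Size with no drug effect.** Let p be the risk of a first event in 12 weeks, the same on both treatments. The documents give no such risk, so p is assumed. The placebo column expects p. The ataluren column expects:

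- all complete the extension, constant risk: 1 − (1 − p)^9
- half enter and complete it: 0.5 × [1 − (1 − p)^9] + 0.5 × p
- all complete, hazard falls to a quarter after 12 weeks: equivalent time 12 + 0.25 × 96 = 36 weeks, giving 1 − (1 − p)^3

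| Placebo (p) | All complete | Half enter | Hazard falls to a quarter |
|---|---|---|---|
| 5% | 37.0% | 21.0% | 14.3% |
| 10% | 61.3% | 35.6% | 27.1% |
| 20% | 86.6% | 53.3% | 48.8% |

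Section 7.1 reports 7 + 8 = 15 subjects randomized. With 15 per column, p = 10%, full completion and the columns treated as independent, simulation gives a 99.9% chance that ataluren shows the higher percentage. In a 12 v 12 week table the figure is 37.6%, with placebo equally likely to be higher and the rest ties.

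**Does patient-time repair it?** At constant hazard, yes: first events divided by time to first event gave simulated ataluren/placebo ratios of 0.99, 1.00 and 1.00 at p = 5%, 20% and 50%. If the hazard falls to a quarter after 12 weeks, no: the all-event rate over 108 weeks would be 36/108 = one third of the placebo rate with no drug effect, which flatters ataluren. A patient-year rate therefore suits a single ataluren column. It does not rescue a comparison with placebo.

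**Denominator.** If the total means all randomized subjects, someone who leaves in Period 1 stays in the denominator of a treatment never received. This touches the Week 28 window and, by the same logic, Weeks 17–28. It is a small effect. For illustration, 3 subjects with an event is 3/15 = 20.0%, or 3/14 = 21.4% if one of the 15 was never exposed.

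**Exposure formula.** Section 7.5.3 takes last dose minus first dose plus 1 day. For an extension completer who had ataluren first, that is about 124 weeks, including 4 weeks of washout and 12 of placebo. Time on ataluren is 124 − 16 = 108 weeks.

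**The case against.** A reader might infer that the AE tables in general compare 108 weeks with 12, or that the controlled safety comparison is biased. The documents do not support that. The Week 12 and Weeks 17–28 summaries are equal in planned exposure, Week 28 is nearly so, and Weeks 29–124 has no comparator to distort. Much of the sensible structure is already planned.

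Nor do the documents say outright that the Week 124 table has a placebo column beside masked plus open-label ataluren. Treatment group is not defined for a table that spans the crossover. If it means randomized sequence, planned exposure is the same in both columns and the nine-fold contrast disappears. That objection stands as a limit on certainty, but it does not make the table useful: each sequence column would mix ataluren and placebo events, with no placebo column left. Either reading calls for a definition.

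The largest figures also assume that everyone completes the extension at constant risk. Section 7.1 makes extension numbers depend on who completes and remains eligible. The gap narrows under the other assumptions but keeps its direction.

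Finally, AEs are not tested, no decision rule rests on this table, and the exposure bands let a reader see the long ataluren follow-up. This lowers the severity. It does not make the percentages comparable. On the denominator, the total may simply mean the column total, and Section 1.5 expects few dropouts, so that part is minor.

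**Conclusion.** The point holds for one of the five planned windows, the cumulative summary to Week 124, on condition that its columns mean treatment received. That is the natural reading of 7.6.1 but is not spelled out. On that reading, crude percentages would make ataluren look worse with no drug effect, for any event with a background rate. For an assumed 10% risk per 12 weeks, the distortion ranges from 10% v 27% to 10% v 61%, depending on extension uptake and how the hazard changes with time.

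The equal-exposure comparison within the masked periods remains available. Apart from the washout and the small denominator effect, it is sound. Severity is moderate.

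**What to change.** In Sections 7.6 and 7.6.1:

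1. Define AE columns as treatment received at onset, with subjects exposed to that treatment as denominator. State where events starting in the Week 12–16 washout are shown.
2. Compare ataluren with placebo only over the two masked periods.
3. Show any window that includes the extension (to Week 124, Weeks 29–124) as a single ataluren column, with events and first events per patient-year of actual ataluren exposure. Exclude washout and placebo time, which the Section 7.5.3 formula does not do. For first events, count time to the first event.

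The cost is table-shell wording and one exposure-adjusted table. It needs no new data beyond the AE and dosing dates already collected.

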7.6.2 Laboratory Parameters

Changes in clinical laboratory tests from Baseline (last measurement prior to randomization) and laboratory marked abnormalities (laboratory AEs) using pre-defined abnormality criteria will be descriptively summarized. In the by-subject analysis, a subject having the same abnormality more than once will be counted only once based on the worst severity grade observed.

7.6.3 Other Parameters

Height, weight, vital signs, and physical examination data will be descriptively summarized. Concomitant medications will be summarized.

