In vitro data indicate that ataluren is an inhibitor of UGT1A9, organic anion transporter (OAT)-1, OAT3, and OATP1B3. Caution should be exercised when ataluren is co-administered with drugs that are substrates of UGT1A9 (eg, propofol, mycophenolate mofetil), OAT1, OAT3, or OATP1B3 (eg, oseltamivir, acyclovir, ciprofloxacin, captopril, furosemide, bumetanide, valsartan, pravastatin, rosuvastatin, atorvastatin, pitavastatin) because of the risk of increased concentration of these drugs. The investigator is encouraged to consult the PTC Therapeutics medical monitor or designee with questions relating to specific drugs and their potential for interactions with ataluren.

Ataluren was evaluated in safety pharmacology studies and was found to have no effects on the cardiovascular system, respiratory system, or central nervous system. In the toxicology program, the major findings observed were species-specific (ie, observed only in one species). These findings included kidney findings in mice (nephrosis, predominantly in the distal nephron, reversible following cessation of dosing) and adrenal gland cortical findings in dogs (lymphohistiocytic infiltrates with focal parenchymal cell degeneration in regions responsible for synthesis of glucocorticoids). Chronic studies were conducted in weanling rats and dogs to support dosing in children as young as 2 years of age. Ataluren was not genotoxic, and was not teratogenic in rats and rabbits. In rats and rabbits, fetal toxicity was observed only at

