1.5.2 Research Risks & Benefits

1.5.2.1 Risk of Study Drug

Ataluren has been studied in previously completed as well as ongoing clinical trials for other diseases. The side effects of ataluren indicated in trials include vomiting, nausea, abdominal pain, headache, pyrexia, rhinitis, and sinusitis. All subjects will be closely monitored for adverse events (AEs) throughout the study.

CYP Inhibition

Ataluren is a weak inhibitor of CYP2C9 and CYP2C8. Clinical drug interaction studies between ataluren and CYP2C8 and CYP2C9 substrates have not been conducted. Ataluren has the potential to increase the plasma concentration of drugs that are primarily metabolized by CYP2C8 or CYP2C9, which includes drugs with a narrow therapeutic index that are substrates of CYP2C8 or CYP2C9. The effects of other concomitant AEDs and other drug levels metabolized by these enzyme systems are not known, but it may increase their levels leading to potential toxicities. Therefore, AED plasma levels will be measured at Baseline (pre-dose of AED) and 6 weeks following the first ataluren dose in each Treatment Period (ie, Visit 3/Week 6 and Visit 6/Week 22), Visit 5/Week 16, , Visit 7/Week 28 [EOS], and Visit 8/Week 52, and Visit 11/Week 124 [EOT]. Antiepileptic drugs may be adjusted as needed based on signs and symptoms of toxicity and/or changes in drug levels.

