3.1 Inclusion Criteria

Subjects who will be selected for this study must meet the following criteria:

1. Age \geq 2 years old and \leq 12 years old, male or female, at Week 0 (at time informed consent/assent is signed)
2. Documentation of a diagnosis of Dravet syndrome or CDKL5 deficiency resulting from a nonsense mutation in 1 allele, as evidenced by medical records, genetic testing, and the following clinical feature:
 - a. Failure to control seizures despite appropriate trial of 2 or more AEDs at therapeutic doses
3. Between 1 to 3 baseline AEDs at stable doses for a minimum of 4 weeks prior to enrollment (ie, Screening visit)
 - a. Vagus nerve stimulator (VNS), ketogenic diet, and modified Atkins diet do not count towards this limit but must be unchanged for 3 months prior to enrollment (Screening).
4. VNS must be on stable settings for a minimum of 3 months prior to the Baseline visit
5. If on ketogenic or modified Atkins diet, must be on stable ratio for a minimum of 3 months prior to the Baseline visit
6. Written consent obtained from the subject or subject's legal representative must be obtained prior to performing any study procedures
7. Minimum of 6 convulsive or drop seizures with duration $>$ 3 seconds over the 4 weeks of diary screening prior to randomization and \geq 6 convulsive or drop seizures with duration $>$ 3 seconds during the 4 weeks from Screening to Baseline.

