3.3 Subject Recruitment and Screening

Approximately eight nonsense mutation Dravet syndrome subjects and 10 nonsense mutation CDKL5 subjects will be recruited for the study from the Principal Investigator or sub-investigator's clinical practice at New York University Comprehensive Epilepsy Center (NYU CEC). All subjects will have had diagnoses confirmed by a geneticist. If this has not been done, then they will be referred to a neurogeneticist at New York University Langone Medical Center (NYULMC). During a routine visit, subjects who meet criteria for the study (or their parents/legal guardians) will be asked if they would like to participate in the study. Male and female subjects of any ethnicity between ages of 2 and 12 (inclusive) will be assessed for inclusion. During the routine visit, the investigator will inform each prospective subject/parent/legal guardian of the nature of the study, and explain the potential risks and study-related procedures. If the subject/parent/legal guardian agrees, they will be given the informed consent documents to read and sign prior to starting any study procedures. Only the Principal Investigator, sub-investigators, and other research personnel listed on the study will have access to subject information. Once the study subject/parent/legal guardian has signed the informed consent, the investigator will explain the study during the routine visit and inform the subject and surrogate that a capacity assessment will be performed to determine whether the subject is capable of providing an informed decision to participate in the study. At this time, a capacity assessment will be conducted if the subject does not refuse the assessment. Capacity will be assessed through neurological examinations and neuropsychology reports conducted by the physician as well as learning and/or development delays that have been documented. If there is already documentation of lack of capacity, no assessment will be needed. If it has been determined by the investigator that the subject has capacity, they will be given the assent form to review. The investigator will go over the study as described in the assent form including study visits and procedures. The subject will be allowed time to ask questions. If the subject is comfortable, then they can sign the assent. All documentation will be placed in the study binder and documented in the study visit note. A copy of the informed assent and consent documents will be given to the subject and the subject's parent/legal guardian. Screening procedures may begin. The Screening Period is 4 weeks, during which study candidates must complete a diary documenting the frequency and duration of convulsive or drop seizures.

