6 SCHEDULE OF EVENTS AND STUDY PARAMETERS

6.1 Schedule of Events

The types and timing of data to be recorded are summarized in Table 1.

Table 1 Schedule of Events

Protocol Activities	Screening ^a	Treatment Period 1			4-Week Washout/ Crossover	Treatment Period 2 ^b		EOS Visit ^c or Begin Open- Label	Open-Label Extension ^d			End of Treatment	Follow Up ^e
		0	6	12		16	22		28	52	76		
Week (±6 days)	-4 (Wk -4 to Wk 0; Day -28 to Day 1)	0	6	12		16	22	28	52	76	100	124	128
Visit	1	2 ^f	3	4		5	6	7	8 ^g	9	10	11	12
Informed consent/assent	X												
Medical history	X												
Serum viral screen	X												
Physical examination	X	X		X		X		X	X	X	X	X	X
Height and weight	X	X	X	X		X	X	X	X	X	X	X	X
Vital signs	X	X	X	X		X	X	X	X	X	X	X	X
Seizure data diary provided	X	X	X	X		X	X	X	X	X	X	X	
Seizure data diary collected		X	X	X		X	X	X	X	X	X	X	X
Study drug dispensed		X ^h	X			X ^h	X	X ^h	X ^h	X ^h	X ^h		
Study drug administration		X ⁱ				X ⁱ		X ⁱ					
Study drug compliance and return			X	X			X	X	X	X	X	X	
Adverse events	X	X	X	X		X	X	X	X	X	X	X	X
Concomitant medications	X	X	X	X		X	X	X	X	X	X	X	X

Protocol Activities	Screening ^a	Treatment Period 1			4-Week Washout/ Crossover	Treatment Period 2 ^b		EOS Visit ^c or Begin Open- Label	Open- Label Extension ^d			End of Treatment	Follow Up ^e
		0	6	12		16	22		28	52	76		
Week (±6 days)	-4 (Wk -4 to Wk 0; Day -28 to Day 1)	0	6	12		16	22	28	52	76	100	124	128
Visit	1	2 ^f	3	4		5	6	7	8 ^g	9	10	11	12
Blood for CBC, CMP, LFTs, BUN, creatinine levels, serum HCG ^j	X	X		X		X		X	X	X	X	X	
Blood for plasma PK for ataluren ^k			X			X	X						
Blood for plasma PK for AED assessment ^l		X	X			X	X	X	X			X	
Urinalysis	X	X		X		X		X	X	X	X	X	
Behavior Assessment System for Children		X		X		X		X				X	
Vineland Adaptive Behavior Scales		X		X		X		X				X	
Quality of Life in Childhood Epilepsy		X		X		X		X				X	

Abbreviations: AED = antiepileptic drug; BUN = blood urea nitrogen; CBC = complete blood count; CMP = comprehensive metabolic panel; EOS = end of study; EOT = End of treatment; F/U = follow-up; HCG= human chorionic gonadotropin; LFTs = liver function tests; PK = pharmacokinetics; wk = week

a. Screening will occur from Week -4 to Week 0 (ie, 28 days). The ±6 day visit window is not applicable to the Screening Period.

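### Height, weight and creatinine in children aged 2 to 12 are summarised without standardisation for age or size, so over the uncontrolled extension normal growth can mask poor growth and suggest a decline in kidney function

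*Combined protocol and SAP*

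**What the plan says.** Section 7.6.3 gives the whole plan for growth and vital signs in one clause: "Height, weight, vital signs, and physical examination data will be descriptively summarized". It names no metric, no age reference and no comparison point.

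Creatinine comes under Section 7.6.2, which plans descriptive summaries of "Changes in clinical laboratory tests from Baseline (last measurement prior to randomization) and laboratory marked abnormalities (laboratory AEs) using pre-defined abnormality criteria". The abnormality criteria are not set out. Baseline is fixed before randomization, so a Week 124 table under this section shows change over the whole time on study.

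The population is growing children. Section 3.3 states: "Male and female subjects of any ethnicity between ages of 2 and 12 (inclusive) will be assessed for inclusion". Section 1.5 gives a 28-week crossover followed by a 96-week open-label extension to Week 124, and the notes to Table 1 say that everyone in the extension receives ataluren.

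The schedule in Section 6.1 lists "Blood for CBC, CMP, LFTs, BUN, creatinine levels, serum HCG" at Screening and Weeks 0, 12, 16, 28, 52, 76, 100 and 124. Height and weight are recorded at each of those visits. GFR is mentioned once, in Section 5.1.1, as an optional test in the work-up of an individual child. No section plans z-scores, percentiles, growth velocity or estimated GFR as a summary.

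**The concern.** Creatinine, height, weight and blood pressure all shift with age and body size in this age range. A raw change therefore mixes growth with any drug effect. During the crossover each child also has a placebo period. In the extension nothing separates the two, and that is where slowly developing harm would be looked for.

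The protocol gives reasons to look. Section 1.3 reports "kidney findings in mice (nephrosis, predominantly in the distal nephron, reversible following cessation of dosing" among its major toxicology findings. Section 1.5.2.1 says "The side effects of ataluren indicated in trials include vomiting, nausea, abdominal pain", and such effects could slow weight gain. Section 3.6.1 lists impaired renal function among possible reasons for discontinuing study drug.

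At stake is how the long-term safety tables read. A mean weight that rises looks reassuring even if the children gain less than they should. A mean creatinine that rises looks like kidney decline even if filtration is unchanged.

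**Working it through.** **Inputs from the documents.** Crossover 28 weeks and extension 96 weeks (Section 1.5); one masked period of 12 weeks; ages 2 to 12; Baseline before randomization (Section 7.6.2).

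**Assumptions not in the documents.** Height velocity 5-7 cm/year, starting height 90-140 cm, creatinine proportional to height at constant filtration, normal weight gain 2-3 kg/year. The documents give no growth or creatinine figures, so ranges are shown.

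**Duration.** 28 + 96 = 124 weeks, which matches the plan's Week 124; 124/52 = 2.385 years. This is time on study. Scheduled ataluren dosing within it is at most 12 + 96 = 108 weeks.

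**Creatinine, Baseline to Week 124.** Height gain = velocity × 2.385 = 11.92 to 16.69 cm. At constant filtration the relative rise in creatinine is height gain / starting height:
- smallest: 11.92/140 = 8.5%
- largest: 16.69/90 = 18.5%

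Read as kidney function, the apparent fall is 1 − 1/(1 + rise): 1 − 1/1.085 = 7.8% to 1 − 1/1.185 = 15.6%.

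**Creatinine, Week 28 to Week 124.** 96/52 = 1.846 years, so height gain is 9.23 to 12.92 cm. With 90-140 cm taken as the height at Week 28, the rise is 9.23/140 = 6.6% to 12.92/90 = 14.4%.

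**Weight.**

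| Window | Normal gain | Gain at half the normal rate |
|---|---|---|
| Baseline to Week 124 | 2 × 2.385 = 4.8 kg to 3 × 2.385 = 7.2 kg | 2.4 to 3.6 kg |
| Week 28 to Week 124 | 2 × 1.846 = 3.7 kg to 3 × 1.846 = 5.5 kg | 1.8 to 2.8 kg |

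The raw change is positive in both columns, so its sign does not distinguish the two children.

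**One 12-week masked period.** 12/52 = 0.231 years: 1.15 to 1.62 cm, a creatinine rise of 1.15/140 = 0.8% to 1.62/90 = 1.8%, and a normal weight gain of 0.5 to 0.7 kg.

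**What standardised measures would show under the same assumptions.** Change in height z-score stays near zero for the normal grower and falls for the slow grower. Height-adjusted estimated GFR does not change when filtration is constant.

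**The case against.** The strongest reply has five parts.

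- **Silence is not a wrong analysis.** Section 7.6.3 excludes no z-score, and the abnormality criteria in Section 7.6.2 may be age-specific. This stands for the criteria: whether growth drift would produce a marked abnormality cannot be told. But age-specific criteria would help to flag individuals and would not correct the mean-change table, which Section 7.6.2 does specify.
- **There is other evidence of harm.** Urea, the metabolic panel and urinalysis are collected at the creatinine visits. Section 5.1.1 describes individual renal review, Section 7.6.1 tabulates adverse events by Preferred Term and severity, and Section 8.2.3 makes laboratory abnormalities suggesting organ toxicity reportable. This stands. A reader might infer that the plan cannot tell kidney harm from growth at all; these sections do not support that.
- **The window should be 96 weeks.** For change from Week 28 that is right, and the drift is then about 7-14%. But the plan's own Baseline precedes randomization, so its Week 124 table would carry the full 8-19%.
- **General-population growth may not apply.** Section 1.1.1 says that many children with CDKL5 never walk independently. This stands, and it limits both the size of the drift and the reading of any z-score or estimated GFR.
- **Little depends on it.** Section 1.3 calls the toxicology findings species-specific and of low human risk. Section 7.1 reports 7 + 8 = 15 children randomised, and standardised values could be derived afterwards. These points lower the priority. They do not make the raw summaries easier to interpret, and choosing the metric beforehand costs almost nothing.

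**Conclusion.** The point holds as a low-cost improvement to safety reporting. In the extension, Weeks 28 to 124, the planned summaries of creatinine and body size move with normal growth and have no control to remove it. Under the stated assumptions the creatinine drift is about 8-19% from Baseline to Week 124 and about 7-14% from Week 28. A child gaining half the expected weight shows about +2.4 to +3.6 kg from Baseline, or about +1.8 to +2.8 kg from Week 28. The direction holds for any child who grows. The sizes depend on assumed growth rates and on creatinine being proportional to height.

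A reader might also infer that the masked comparison is compromised. It is not: the drift within a 12-week period is about 1-2% in creatinine, and each child is scheduled for both treatments. The primary seizure analysis is untouched. Nothing here shows that ataluren affects growth or kidneys in these children, or that monitoring of individual children is inadequate.

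**What to change.** In Section 7.6.3, add change in age- and sex-standardised z-scores for height, weight and blood pressure, measured from Baseline and, for the extension, also from Week 28. In Section 7.6.2, add change in height-adjusted estimated GFR, for example by the bedside Schwartz formula, computed from the creatinine and height of the same visit. Name the reference standards and the formula, and show these results beside the raw values.

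The cost is a few sentences and some derived variables. Height, weight, blood pressure, creatinine, age and sex are already available, so no visit or sample is added.

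The downside is that population references and creatinine-based estimates may misstate levels in children with severe motor impairment. The text should say that within-child change, and not the level, is to be interpreted. No dose, stopping rule or clinical management rule changes.
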